#### 5.4.5 Dose Increase after Dose Reduction

The dose of quizartinib will be increased by one level at a time in patients whose dose has once been reduced. However, if the dose of quizartinib is reduced associated with

Grade 3 QTcF prolongation, the dose may not be increased. If the dose of quizartinib is reduced associated with Grade 2 QTcF prolongation, the dose may be increased to the dose before dose reduction if QTcF prolongation recovers to Grade 1 or less severe after treatment at a reduced dose for at least 28 days.

If the dose of quizartinib is reduced due to AEs, the dose must not be increased unless the concerned AE recovers to Grade 1 or less severe. If the dose of quizartinib is reduced because concomitant use of a strong CYP3A4 inhibitor is started during the study, quizartinib may be administered at the dose before dose reduction after a 7-day washout when the concomitant use of the strong CYP3A4 inhibitor is discontinued.

# 5.5 Method of Assessing Treatment Compliance

The investigators will evaluate the patient's treatment compliance with the study drug based on the information in the dosing diary filled out by the patients and the number of tablets returned. Administration of the study drug will be recorded in the case report form (CRF)/Drug Accountability Record. If there are no returned tablets, the investigators should ask the patient whether any tablets were disposed of, rather than taken orally.

As the information on administration of the study drug, the dose of the study drug, date and time of administration, start date of treatment, date of discontinuation of treatment, date of interruption of treatment, date of resumption of treatment, reason for interruption of treatment, etc. will be clearly documented in the CRF.

#### 5.6 Concomitant Medications

### 5.6.1 Investigation Items

All concomitant drugs and other therapies than the study drug that are used and transfusions introduced during the period from the day of the first dose of the study drug to the day of post-treatment observation will be recorded in the CRF. For concomitant drugs or therapies, or transfusion that is newly started after the day following the last dose of the study drug, those used only for the treatment of AEs will be recorded in the CRF. Concerning the details of the items to be entered, refer to Section 6.2.

# 5.6.2 Prohibited Concomitant Drugs, Restricted Concomitant Drugs, and Drugs to Be Coadministered with Care

### 5.6.2.1 Prohibited Concomitant Drugs

The drugs listed below should not be used concomitantly with the study drug from the

day of informed consent to the study through the day of post-treatment observation. It is, however, allowed to concomitantly use hydroxycarbamide at doses of up to 2 g/day only during the period from 14 days before the first dose of quizartinib to 4 days after the start of treatment with quizartinib. If hydroxycarbamide has been used at least 15 days before the start of the first dose of quizartinib, the first dose of quizartinib may be started with a 1-day washout.

- 1) Antiarrhythmic drugs, antibacterial, antifungal, psychotropic, and other drugs that may potentially prolong the QT/QTc interval (excluding medically unavoidable cases in the opinion of the investigators)
- 2) Strong or moderate CYP3A4 inducers
- 3) Crude drugs and food products with CYP3A4-inhibiting or -inducing properties (eg, foods and beverages containing St. John's wort or grapefruit)
- 4) Anticancer treatments other than quizartinib (Concomitant use of hydroxycarbamide during the aforementioned period is allowed.)
- 5) Investigational drugs other than quizartinib, and investigational devices

## 5.6.2.2 Drugs to Be Coadministered with Care

The following points should be noted during the period from the day of informed consent to the day of post-treatment observation.

- During treatment with quizartinib, use of substrates of P-glycoprotein should be avoided as far as possible.
- Concomitant use of strong CYP3A4 inhibitors is not prohibited, but should be
  avoided because it is required to start treatment with quizartinib at a reduced dose.
  Moderate or weak CYP3A4 inhibitors (fluconazole etc.) may be used concomitantly
  without reducing the dose of quizartinib.

#### <Rationale>

These specifications are provided for proper safety evaluation of quizartinib.

Quizartinib and AC886 are mainly metabolized by CYP3A4. If the need arises to use drugs that may potentially prolong the QT/QTc interval or strong or moderate CYP3A4 inducers by necessity for the prevention or treatment of infection during the study, concomitant use of these drugs with quizartinib should be avoided.

In addition, in vitro data indicate that quizartinib inhibits P-glycoprotein. For this reason, concomitant use of quizartinib with substrates of P-glycoprotein should be avoided as far as possible. Concomitant use of quizartinib with P-glycoprotein

substrates may increase the blood concentrations of the P-glycoprotein substrates.

# 5.7 Subject Withdrawal/Discontinuation

## 5.7.1 Discontinuation Criteria for Treatment with the Study Drug

If any of the following criteria apply, the investigators should immediately discontinue treatment with the study drug and proceed to the post-treatment observation period.

- 1) Overt disease progression is observed.
- 2) Grade 4 QTcF prolongation is observed.
- 3) The investigators decide that continued treatment with the study drug is no longer beneficial to the patient based on AEs and the results of laboratory test values.
- 4) LVEF is less than 45%.
- 5) The investigators decide to introduce HSCT.
- 6) Treatment with quizartinib is interrupted for longer than 14 days.
- 7) The patient is found to deviate from the inclusion criteria or fit the exclusion criteria after registration.
- 8) Pregnancy is found after registration.
- 9) The sponsor decides to discontinue the study.
- 10) The patient requests for withdrawal from treatment with the study drug.
- 11) Other circumstances why the study cannot be continued in the opinion of the investigators

If treatment with the study drug is discontinued, the investigators should take appropriate actions for the patients, and then perform tests/assessments specified in "6.3 Procedures When Treatment with the Study Drug Is Discontinued," and record the obtained information in the CRF. The date of discontinuation of treatment with the study drug and the reason for discontinuation will also be recorded in the CRF. The date of discontinuation of treatment with the study drug is not the date when the AE leading to discontinuation occurs, but the date when the investigators determine discontinuation of the treatment.

# 5.7.2 Reasons for Discontinuation during the Post-treatment Observation Period and the Follow-up Period

If the study is discontinued during the patient's post-treatment observation period or the follow-up period for the following reasons, the date of discontinuation and the reason for discontinuation will be recorded in the CRF.

- 1) The patient died.
- 2) The patient requests for withdrawal from the study during the post-treatment observation period or the follow-up period.
- 3) The patient is lost to follow-up.
- 4) The sponsor decides to discontinue the study.
- 5) Other

#### 5.7.3 Withdrawal Procedures

If a patient is withdrawn from the study, the investigators will complete and report the observations as thoroughly as possible up to the date of withdrawal including the date of last administration and the reason for withdrawal.

If the patient is withdrawn due to an AE, the investigators will follow the patient as far as possible until the AE has resolved or stabilized.

All patients who are withdrawn from the study should complete protocol-specified withdrawal procedures.

#### 6. STUDY PROCEDURES

Study procedures specified in the protocol are shown in "Table 6-1 Schedule of Study Procedures."

In the study, the period from the day of informed consent through the last day of the follow-up period is defined as the "study period" for each patient. However, if a patient has difficulty to attend the follow-up at the study center for reasons including transfer to another hospital or he/she refuses to visit the study center after the final dosing of quizartinib, then the study period for the patient will be terminated on the relevant day.

Table 6-1 Schedule of Study Procedures

	Screening (≤ 14 Days	Cycle 1		Cycle 2		Cycle 3	Cycle 4 and Thereafter	At	Post treatment Observation	Follow		
	before Registration)	Day 1	Day 2 and 8	Day 15	Day 16	Day 1	Day 15	Day 1	Day 1	Withdrawal	30 Days after the Last Dose	up
Acceptable limit (unit: days)			Day 2: Scheduled Day Day 8: ±1	±1	(Must Be the Day Following Day 15)	±3	±1	±3	±3	3 to +7	+15	Every 3 Months
Informed consent	•											
FLT3 ITD test	•*1											
Administration of quizartinib (at the study center)		•*2	•*2	•*2	•*2	•*2	•*2	•*2	•*2			
Medical history/complications	•											
Vital sign measurement	•	•	•	•		•	•	•	•	•	•	
ECOG PS/body weight	•	•				•		•	•	•	•	
Height	•											
Laboratory tests (hematology, blood chemistry, urinalysis)	•	•*3	•*3	•*3		•*3	•*3	•*3	•*3	•	•	
Pregnancy test	•											
HIV antibody	•*4											
12 lead ECG	•*5	•*5	●* 	◆*5		•*5		*5	●* 	●* 		
X ray examination	•			•		•	o (as n	eeded)				•
MUGA scan or echocardiography	•* 						o (as n	eeded)				
Assessment of bone marrow findings (tumor assessment)	•*7					•*7		•* 	•*7	*7		
Measurement of drug concentrations		•*8	•*8	•*8	•*8	•*8		•*8				
Inhibitory activity on phosphorylated FLT3 and c Kit proteins		•* 	•*9	•*9		●* 						
AEs		●*10										
Assessment of concomitant drugs and therapies		•										
Investigation of survival status Other leukemia treatment etc.											•	•

 FLT3 ITD levels will be measured using a bone marrow specimen or peripheral blood. The collected bone marrow specimen or peripheral blood will immediately be submitted to the specimen collection agency.

 Quizartinib will be administered on Days 1, 2, 8, 15, and 16 of Cycle 1, Days 1 and 15 of Cycle 2, Day 1 of Cycle 3, and Day 1 of Cycle 4 and subsequent cycles at the study center. Quizartinib may be administered at home on the other days.

- 3) To be measured before administration of the study drug.
- 4) To be performed within 120 days before registration.
- ECG will be measured three times (triplicate ECGs) at each of the following time points. Triplicate ECGs will be obtained at least once weekly for the first 2 weeks after increasing the dose of quizartinib to carefully confirm the QTcF interval.

  Screening, Day 1 of Cycle 1 (before administration of the study drug and at 2, 4, and 6 hours after the end of administration of the study drug), Day 2 and Day 8 of Cycle 1 (before administration of the study drug and at 2 to 4 hours after the end of administration of the study drug), Day 15 of Cycle 1 (before administration of the study drug and at 2, 4, and 6 hours after the end of administration of the study drug, [if the dose of quizartinib is not increased on Day 16 of Cycle 1]: before administration of the study drug and at 2 to 4 hours after the end of administration of the study drug), Day 1 of Cycle 3 (before administration of the study drug and at 2 to 4 hours after the end of administration of the study drug), Day 1 of Cycle 3 (before administration of the study drug and at 2 to 4 hours after the end of administration of the study drug on Day 1 of each cycle)
- 6) A multiple gated acquisition (MUGA) scan or echocardiography must be performed at screening except in case LVEF is 45% or more within 1 month before registration.
- 7) It is desirable to assess bone marrow findings with specimens obtained by both bone marrow aspiration and biopsy; however, bone marrow biopsy may be skipped if the antitumor effect can be evaluated adequately only by bone marrow aspiration in the opinion of the investigators. Assessment of bone marrow findings will be performed at screening (it is desirable to obtain the specimen within 14 days before registration; however, the specimen collected before the time may be used with the consent of the medical monitor etc.), on Day 1 of Cycle 2 and subsequent cycles, at the time of discontinuation of the study, and other time points if assessment is considered necessary by the investigators. For patients achieving CR, CRp, or CRi, bone marrow findings will be assessed every 3 cycles.
- 8) A plasma specimen for pharmacokinetic measurement will be collected at the following specified time points. If ECG and blood collection for pharmacokinetics (PK) are scheduled at the same time, blood collection for PK will be performed immediately after the end of ECG.

  Day 1 of Cycle 1 (before administration of the study drug and at 1, 2, 4, 6, and 24 hours after the end of administration of the study drug), Day 8 of Cycle 1 (before administration of the study drug and at 1, 2, 4, 6, and 24 hours after the end of administration of the study drug), Day 1 of Cycle 2 ([if the dose of quizartinib is increased on Day 16 of Cycle 1]: before administration of the study drug and at 1, 2, 4, 6, and 24 hours after the end of administration of the study drug, [if the dose of quizartinib is not increased on Day 16 of Cycle 1]: before administration of the study drug and at 2 to 4 hours after the end of administration of the study drug), and Day 1 of Cycle 3 (before administration of the study drug and at 2 to 4 hours after the end of administration of the study drug).
- 9) A specimen for measurement of inhibitory activity on phosphorylated FLT3 and c Kit proteins will be collected at the following specified time points.

  Day 1 of Cycle 1 (before administration of the study drug and at 2, 4, and 6 hours after the end of administration of the study drug), Day 8 of Cycle 1 (before administration of the study drug), and Day 1 of Cycle 2 (before administration of the study drug).
- 10) Only information on SAEs will be collected during the period from the day of informed consent to before the first dose of the study drug.

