## 6.6 Follow-up

The following information will be confirmed every 3 months after assessment during the post-treatment observation period (confirmation by phone is allowed).

- Investigation of survival status
- Post treatment for AML after discontinuation of treatment with quizartinib
- Presence or absence of relapsed AML, and if present, the date of relapse

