### 6.7 Definition of the Study Period

The study period for each patient is from the time of informed consent to the end of the follow-up assessment.

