# 7.4 Secondary Efficacy Endpoints

The secondary efficacy endpoints of this study are as follows.

- Best response
- Response rate
- Overall survival (time from registration to death)
- Event-free survival (time from registration to progression, relapse, or death, whichever occurs first)
- Leukemia-free survival (time from first achievement of CRc to relapse or death, whichever occurs first)
- Transplantation rate (proportion of patients who start HSCT immediately after the end of treatment with the study drug without receiving other treatment for AML)

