#### 11.3.1.2 Secondary Efficacy Analyses

For the best response and the response rate, frequency tables will be prepared, and the 95% CI will be calculated.

For OS, event-free survival, and leukemia-free survival, Kaplan-Meier curves will be prepared, and medial survival and the 95% CI will be calculated using the method of Brookmeyer and Crowley.

For the transplantation rate, frequency tables will be prepared, and the 95% CI will be calculated.

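### Section 6 ends follow-up when a patient transfers or declines site visits, although Section 6.6 needs only a phone call; survival and relapse may be informatively censored and later transplants may go unconfirmed

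*Combined protocol and SAP*

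**What the plan says.** Section 6 runs each patient's study period from consent through the last day of follow-up and then makes an exception. After the final dose, "if a patient has difficulty to attend the follow-up at the study center for reasons including transfer to another hospital", or if the patient refuses to visit, "then the study period for the patient will be terminated on the relevant day".

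Section 6.6 sets the later follow-up: survival status, post treatment for AML and relapse, every 3 months, with the note that "confirmation by phone is allowed". Section 6.7 restates the study period without the exception: "The study period for each patient is from the time of informed consent to the end of the follow-up assessment".

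The endpoints that depend on this follow-up are in Section 7.4:
- OS: "Overall survival (time from registration to death"
- EFS and LFS, which need relapse dates
- transplantation rate: "proportion of patients who start HSCT immediately after the end of treatment with the study drug without receiving other treatment for AML"

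Section 11.3.1.2 gives the analysis of the time-to-event endpoints: "For OS, event-free survival, and leukemia-free survival, Kaplan-Meier curves will be prepared". It states no censoring rule.

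**The concern.** The trigger in Section 6 is attendance at the center, but the data needed after the post-treatment observation do not require attendance. A patient who has moved hospital, can be reached and has not withdrawn consent is neither a withdrawal nor a loss to follow-up; Section 5.7.2 lists both of those separately. A site that applies Section 6 literally would nevertheless stop collecting survival, relapse and transplant data on that patient.

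In relapsed or refractory AML, a move after study drug is plausibly linked to outcome. Some patients go elsewhere for transplant, and Section 1.2.1.2.2 reports that transplanted patients tended to live longer in the earlier lower-dose study. Others go elsewhere for end-of-life care. Kaplan-Meier treats a patient censored at the move as having the same outlook as those who stay.

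The trial has one arm, so no comparator shares the distortion. Section 7.5 also justifies CRc partly because it opens the way to HSCT and longer survival, and these are the data that the exception puts at risk.

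**Working it through.** **The passages side by side**

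| Place | What it requires or keeps |
|---|---|
| Section 6 | Ends the study period on transfer or refusal to visit after the last dose |
| Section 6.6 | Three items every 3 months, phone sufficient |
| Section 6.7 | Study period to the end of follow-up, no exception |
| Section 5.7.1 | A decision for HSCT stops study drug; date and reason go in the CRF |
| Section 6.4 | The 30-day observation is done before post treatment starts |
| Section 6.5 | Name and start date of post treatment are recorded if it starts before that observation is complete |

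The HSCT *decision* is therefore kept, as is HSCT begun early. HSCT that starts after the 30-day observation is normally seen only in the Section 6.6 follow-up, which Section 6 can cut off. No section tells the site to keep phoning after the study period has ended.

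**The plan's own figures**

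The plan states no figure for OS or transplantation rate. Its only design calculation is for CRc. With X1 ~ Bin(25, p) and X2 ~ Bin(16, p):

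P(effective) = P(X1 ≥ 11) + Σ over x = 4..10 of P(X1 = x) × P(X2 ≥ 15 − x)

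This gives 0.0482 at p = 0.235 and 0.8137 at p = 0.42, matching the stated 0.048 and 0.814. Post-treatment follow-up does not enter this rule.

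**Transplantation rate (illustration)**

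Section 1.2.1.2.2 reports 34-35% proceeding to HSCT in the earlier studies. 0.34 × 41 ≈ 14, and 14/41 = 34.1% (exact 95% CI 20.1-50.6%). The share left unconfirmed is an assumption.

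| Unconfirmed | Still confirmed | Rate if only confirmed cases count |
|---|---|---|
| 25% | 14 × 0.75 = 10.5, so 10 or 11 | 24.4% or 26.8% |
| 50% | 14 × 0.50 = 7 | 17.1% |

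**Median OS (illustration)**

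From Section 1.2.1.2.2 (Cohort 2): 35% transplanted, 1-year survival of 39% applied to them, overall median 24.0 weeks. Assuming exponential survival in each group:
- transplanted hazard = −ln(0.39)/52 = 0.0181 per week
- other hazard = −ln[(0.5 − 0.35·e^(−0.0181×24))/0.65]/24 = 0.0361 per week

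Kaplan-Meier medians from 400,000 simulated patients, true value 24.0 weeks:

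| Share of the group censored at transfer | Transplanted, censored at week 12 | Not transplanted, censored 4 weeks before death |
|---|---|---|
| 10% | 23.8 | 25.5 |
| 25% | 23.5 | 28.1 |
| 50% | 22.9 | 34.4 |

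A second model uses one hazard of ln2/24 per week and a treatment-stop time with median 12 weeks. The fraction alive at stop is (1/12)/(1/12 + 1/24) = 2/3, so if 10-30% of those alive at stop transfer, about 7-20% of all patients are censored. Kaplan-Meier then reports about 24 weeks throughout. The true median is 22.7 to 20.4 weeks if the later hazard is three times higher, and 24.7 to 26.7 weeks if it is 0.4 times. With an even mix of the two it is roughly 23.7 to 23.0 weeks.

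Both models show that the direction depends on why patients move.

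**The case against.** Several points on the other side are sound.

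- **Informative censoring is inferred.** The documents state no OS censoring rule, and Section 11.6 leaves detailed methods to a separately prepared SAP. A reader might infer that OS *is* biased. The text supports only that it may be.
- **Transplants elsewhere are not simply lost.** A reader might infer that a responder sent to another hospital is counted as not transplanted. No section says how an unobserved HSCT is counted. Sections 5.7.1 and 6.5 keep the decision and any early start. Because the endpoint counts only HSCT soon after study drug, many relevant patients are already flagged. The gap is confirmation of a later start and of no intervening AML therapy.
- **Section 6.7 can be read as compatible with Section 6**, if Section 6 merely says when follow-up ends for some patients. Section 5.7.2 also has an open category for other reasons, with date and reason recorded, so these patients could be identified.
- **The sizes rest on assumptions.** The 34-35% comes from overseas studies and counts any progression to HSCT, a looser definition than Section 7.4. In the second model, the sampling SD of a median from 41 patients is just under 6 weeks, more than that model's largest gap (24.0 − 20.4 = 3.6 weeks).
- **The affected endpoints are secondary and descriptive.**

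These points limit the claim but do not remove the gap. Identifying who transferred does not recover dates that were never collected. Random error does not excuse an avoidable systematic one. The benign reading, that Section 6 ends only site visits, is not what it says: it ends the study period, which it defines as including follow-up.

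**Conclusion.** The point holds in a limited form. Section 6, as written, stops follow-up in reachable, consenting patients for a reason that Section 6.6 makes unnecessary. The consequence is possible informative censoring of OS, EFS and LFS, and possible non-confirmation of HSCT started after transfer.

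Neither size nor direction can be fixed, because the documents give no transfer or refusal rate and no later hazard. The figures above show only that the effect could be material in plausible settings and small in others. They assume exponential survival, the earlier overseas results as a base, and chosen transfer shares.

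A reader might extend this to the trial's efficacy conclusion. The documents do not support that: the CRc rule and its operating characteristics do not depend on post-treatment follow-up. This is a worthwhile, inexpensive improvement to secondary data, and not a flaw in the primary analysis.

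**What to change.** - **Section 6:** limit the exception to on-site procedures. State that patients who transfer or decline visits continue the Section 6.6 items every 3 months by phone and, where consent allows, through the family or receiving hospital. Ask at each contact for dates of HSCT, relapse and death. Continue until death, withdrawal of consent to follow-up, loss to follow-up or study end.
- **Section 6.7:** align the study-period definition with this.
- **Section 11.3.1.2 or the SAP:** censor OS at the last date known alive.

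Cost: a few extra calls on a schedule and by a route already provided, and a protocol amendment with the approvals in Section 15.7. If the receiving hospital or family is to be contacted, the consent form needs a revised line. Under Section 15.6 that means IRB re-approval and renewed written consent from patients already enrolled. Sample size, significance level and power do not change.
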